### **8.3.2. Adverse Events**

Adverse events reported for subjects participating in this study were primarily graded for severity using the National Cancer Institute's (NCI) Common Terminology Criteria for Adverse Events (CTCAE), version 4.03. For adverse events not covered in the NCI-CTCAE, grading was performed per the criteria outlined in Table 13 of the protocol.

All adverse events will be coded using MedDRA (current version).

All adverse events summaries described below will be presented for both non-SCD and SCD-related TEAEs.

Non-SCD-related TEAE summary tables will exclude sickle cell disease (SCD) related events defined as preferred terms of: acute chest syndrome, pneumonia, sickle cell anemia with crisis, osteonecrosis, and priapism. Additional TEAE tables will summarize the aforementioned SCD related events.

Overall summaries will be presented which include the number of TEAEs and the number and percentage of subjects who experienced at least one TEAE. The summaries will also include TEAEs Grade 3 or greater, TEAEs possibly/probably related to study drug, TEAEs leading to study drug reduction, TEAEs leading to study drug interruption, TEAEs leading to discontinuation of study drug, and serious adverse events (SAEs). TEAEs leading to deaths will be summarized together regardless if they are SCD-related, as cause of death may include multiple TEAEs.

Additional summaries of TEAEs will be provided showing the number and percentage of subjects who experienced at least one TEAE. These summaries will be presented by system organ class (SOC), preferred term (PT) and maximum severity. If a subject reports the same PT multiple times within the same SOC, that PT will only be counted once within that SOC for that subject. As with the PT, if a subject reports multiple conditions within the same SOC, that SOC will only be counted once for that subject. In the summary, SOC will be listed in ascending alphabetical order; PTs will be listed in order of descending frequency for all subjects within each SOC.

The occurrence of TEAEs possibly/probably related to voxelotor will be tabulated by system organ class (SOC), preferred term (PT), and maximum severity. Serious adverse events will be presented by system organ class (SOC), preferred term (PT), and maximum severity.

Grouped terms for rash and abdominal pain will be summarized.

Adverse events recorded in the electronic case report form (eCRF) which began prior to first dose of study drug will not be included in the summary tables.

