10.3.2. Safety Data

All safety assessments will be conducted on the Safety population.

A TEAE is defined as an AE that emerges on or after initiation of study drug (having been absent pretreatment), or an AE that existed pretreatment and worsened on treatment (relative to the pretreatment state). The number and percentage of participants reporting TEAEs will be tabulated by MedDRA® (current version) system organ class and preferred term, severity and relationship to study medication. Serious TEAEs and TEAEs resulting in discontinuation of study drug will be summarized separately.

Concomitant medications will be mapped using the WHODRUG dictionary (current version). The number and percentage of participants taking each concomitant medication will be tabulated.

Analysis of laboratory results will be based on those reported by the local laboratory at each site. Continuous laboratory measurements will be descriptively summarized at each visit for observed values and changes from baseline.

Vital signs and ECG parameters (based on average of triplicate measurements) will be summarized at each visit for observed values and changes from baseline. In addition, QT and QTc intervals will be summarized categorically as number and percentage of participants with abnormal values or increases.

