## 3. STUDY OBJECTIVES FOR PART D

### 3.1. Primary

- To evaluate the safety and tolerability of voxelotor in pediatric subjects with SCD aged 6 months to < 4 years

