## 4. ENDPOINTS FOR PART D

### 4.1. Primary

- Treatment-emergent adverse events (TEAEs) and serious adverse events (SAEs)

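### Part D plans no pooled count of children with any TEAE, Grade 3 or higher TEAE, related TEAE or SAE, although its primary endpoint is TEAEs and SAEs undivided

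*SAP*

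**What the plan says.** The Part D primary objective (Part D SAP 3.1) is "To evaluate the safety and tolerability of voxelotor in pediatric subjects with SCD aged 6 months to < 4 years". The endpoint that serves it is stated without any restriction by relation to sickle cell disease, in protocol 3.9.4.1 and again in the SAP (Part D SAP 4.1: "Treatment-emergent adverse events (TEAEs) and serious adverse events (SAEs").

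Protocol 10.3.2 plans one unsplit tabulation: "The number and percentage of participants reporting TEAEs will be tabulated by MedDRA" system organ class and preferred term, severity and relationship. Serious TEAEs and TEAEs leading to discontinuation get their own summaries, also unsplit.

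Part D SAP 8.3.2 sets a different rule: "All adverse events summaries described below will be presented for both non-SCD and SCD-related TEAEs". It then defines two disjoint sets:

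- "Non-SCD-related TEAE summary tables will exclude sickle cell disease (SCD) related events defined as preferred terms of: acute chest syndrome, pneumonia", followed by sickle cell anemia with crisis, osteonecrosis and priapism.
- "Additional TEAE tables will summarize the aforementioned SCD related events".

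The overall summary comes after that rule. It reports "the number of TEAEs and the number and percentage of subjects who experienced at least one TEAE", together with Grade 3 or higher, related, action-taken and serious categories. The tables by system organ class and preferred term, the related-event tables and the SAE tables also come after it. One exception is stated: "TEAEs leading to deaths will be summarized together regardless if they are SCD-related, as cause of death may include multiple TEAEs".

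Part D SAP section 2 says that its methods supersede those of the protocol where applicable.

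**The concern.** The natural participant-level summary of an undivided safety endpoint is the number and percentage of children with at least one TEAE and with at least one SAE. Under the SAP's rule each such figure appears twice, once per set, and never for the two sets together. A child with a crisis and an unrelated vomiting episode is counted in both sets, so the two percentages cannot be added.

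Assignment to a set is by preferred term, not by the investigator's view of cause. Inpatient hospitalization makes an event serious (protocol 9.2.1), so either set can contribute SAEs. Someone who asks how many children under 4 had any serious event, or any event of Grade 3 or higher, would find no planned number, and this is the part of the study in which safety is the primary question.

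**Working it through.** Part D has no power calculation (Part D SAP 6.1), so there is no stated figure to reproduce. The check is whether the pooled count follows from the two split counts.

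**Inputs.** N = 30 (approximate Part D enrollment, Part D SAP 6.1). At least 10 children are to be 6 months to < 2 years old (protocol 3.1.4), and results are shown by age group and overall (Part D SAP section 8). The documents give no event rates, so every count a and b below is an assumption.

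**Is the overall summary split?** It follows the sentence that splits every summary described below it. The explicit exception for fatal TEAEs would not be needed if the other summaries were already pooled. The SAP names no pooled row elsewhere.

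**What adds up.** Each preferred term is in exactly one set, so numbers of events add across the two sets and preferred-term rows are complete. Numbers of participants do not add in rows that span both sets, including the total for a system organ class with terms in both.

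**Bounds.** Let a children have at least one non-SCD event and b at least one SCD-related event. The number with any event, u, satisfies

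max(a, b) ≤ u ≤ min(N, a + b).

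The bounds coincide only if one count is 0 or N. For N = 30 that is 4 × 31 − 4 = 120 of the 31 × 31 = 961 possible pairs. The widest gap is at a = b = 15: 30 − 15 = 15 children.

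| N | Assumed a, b | u, lowest to highest | Percent | Width (children) |
|---|---|---|---|---|
| 30 | 3, 2 | 3 to 5 | 10.0 to 16.7 | 2 |
| 30 | 6, 5 | 6 to 11 | 20.0 to 36.7 | 5 |
| 30 | 9, 6 | 9 to 15 | 30.0 to 50.0 | 6 |
| 30 | 24, 15 | 24 to 30 | 80.0 to 100 | 6 |
| 30 | 28, 15 | 28 to 30 | 93.3 to 100 | 2 |
| 30 | 15, 15 | 15 to 30 | 50.0 to 100 | 15 |
| 10 | 6, 5 | 6 to 10 | 60.0 to 100 | 4 |

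The first three rows are plausible shapes for SAEs, the next two for any TEAE, the sixth is the worst case, and the last is a small age group. For 6 and 5 SAEs, the exact 95% interval is 7.7% to 38.6% if u = 6 and 19.9% to 56.1% if u = 11.

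**The case against.** **Nothing is lost, and the endpoint is reported.** A reader might infer that the primary endpoint is not produced at all. The documents do not support that. They define the endpoint only as TEAEs and SAEs, name no single proportion as the primary result, and make Part D descriptive with no formal assumptions. Every TEAE and SAE is tabulated in one set or the other. What is missing is a group of participant-level rows.

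**Tolerability is already pooled.** A reader might also infer that discontinuation because of AEs is missing. It is not. Part D SAP 8.3.1 summarizes permanent discontinuation by reason (AE or other), and dose reductions and missed doses due to AEs, with no split. Section 8.1.1 gives reasons for treatment discontinuation. These items are outside this point.

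**The protocol may still apply.** The SAP supersedes only where applicable, and it does not say that it withdraws the protocol's unsplit tabulation. The Part A/B SAP has a section on changes to planned analyses, and the Part D SAP has none. On this reading both displays are owed. That is arguable, but the SAP's rule covers all AE summaries and pools only deaths, so a programmer working from it would not produce the pooled rows. The two texts need reconciling on either reading.

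**Listings could fill the gap.** Protocol 10.3 foresees selected individual listings. If AEs are listed, about 30 children can be counted by hand. That rescues the number but does not make it a planned result.

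**The split is a deliberate convention.** All three SAPs separate SCD-related events, and the separation is useful. This stands, and it is why the split tables should stay as they are.

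**Conclusion.** The point holds as a gap in the specified outputs. The Part D SAP plans no pooled number and percentage of children with any TEAE, any Grade 3 or higher TEAE, any related TEAE or any SAE, and in general the split tables do not determine them.

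The size depends on counts that the documents do not give. With about 30 children the ambiguity is zero when one count is 0 or 30, 2 to 6 children in the other assumed scenarios apart from the worst case, and never more than 15. No data collection and no inference is affected, and the figures can be programmed from data already held.

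The conclusion rests on reading the splitting rule as covering the overall summary, which its position and the stated exception for deaths both support. It does not carry over to Part C as a primary-endpoint problem. Part C SAP 7.3.2 has the same rule, but the Part C primary endpoint is TCD velocity (Part C SAP 3.1.1), and TEAEs and SAEs are safety endpoints there.

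**What to change.** In Part D SAP 8.3.2, add one sentence that the overall summary will also show, regardless of SCD-relatedness, the number and percentage of children with any TEAE, any TEAE of Grade 3 or higher, any possibly/probably related TEAE and any SAE, by age group and overall. Keep the non-SCD and SCD-related tables unchanged. A pooled column in every table is not needed: preferred-term rows would gain nothing from it.

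Reconcile protocol 10.3.2 with Part D SAP 8.3.2 by stating whether the unsplit tabulation by system organ class and preferred term is still intended or is replaced by the split tables.

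The same four rows could be added to the overall summary in the Part C SAP as an optional improvement.

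Cost: one or two SAP sentences and four rows in one Part D table. No new data are needed.

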Among the earliest manifestations of sickle-related organ damage is loss of splenic function in the first two years of life which places children at high risk of sepsis, particularly from encapsulated organisms such as *Streptococcus pneumoniae* and *Haemophilus influenzae*. Furthermore, renal concentrating ability is also impaired and signals the beginning of the decline in renal function that may lead to chronic renal failure and end-stage renal disease. Pain is also an important component of the disease and in young children, presents as dactylitis or hand-foot syndrome and can be the first sign of SCD. The most devastating complication of pediatric SCD is the development of central nervous system (CNS) events. This may present as overt stroke or silent strokes which are subclinical cerebral infarctions detected on brain magnetic resonance imaging (MRI). Almost 50% of the SCD population is pediatric (Farber, 1985) and approximately 11% of SCD patients have clinically apparent strokes before the age of 20 years. The risk of stroke is highest during the first decade, and it is most significant between ages 2 and 5, when it reaches 1.02% per year. In addition to overt strokes, another 17% to 22% of children suffer silent strokes which can produce significant neuropsychological deficits (Ohene-Frempong, 1998; Verduzco, 2009). The pathogenesis of stroke in children with SCD is complex and not fully resolved but in most cases involves occlusion or stenosis of the large intracranial arteries. Histopathology varies, but in general the pattern is one of smooth muscle proliferation with overlying endothelial damage and fibrosis (Rothman, 1986; Koshy, 1990). Smaller arterioles and capillaries show distention, thrombosis and vessel wall necrosis (Tuohy, 1997). Damaged, aberrant red cells adhere abnormally to the vascular endothelium and thereby trigger endothelial cell activation. Endothelial cell activation cascades into further disturbances, including a hypercoagulable state and abnormal vasomotor tone. The greater risk of stroke in young children with SCD may be explained by the higher cerebral blood velocity observed in this population (Powars, 2000).

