4.2. Exclusion Criteria

Any participant who meets one or more of the following criteria will be excluded from participation:

1. Any one of the following requiring medical attention within 14 days of signing the informed consent form (ICF):
 - Vaso-occlusive crisis (VOC)
 - Acute chest syndrome (ACS)
 - Splenic sequestration crisis
 - Dactylitis
2. Requires chronic transfusion therapy.
3. History of stroke or meeting criteria for primary stroke prophylaxis (history of two TCD measurements \geq 200 cm/sec by nonimaging TCD or \geq 185 cm/sec by TCDi).
 - For the potential modification, addition of approximately 20 participants enrolled in Part C, TCD \geq 170 cm/sec by nonimaging TCD or \geq 155 cm/sec by TCDi
4. Transfusion within 30 days prior to signing the ICF.
5. Renal dysfunction requiring chronic dialysis or creatinine \geq 1.5 mg/dL.
6. Hepatic dysfunction characterized by alanine aminotransferase (ALT) $> 4 \times$ upper limit of normal (ULN) for age.
7. Clinically relevant cardiac abnormality, in the opinion of the Investigator, such as:
 - Hemodynamically significant heart disease, eg, congenital heart defect, uncompensated heart failure, or any unstable cardiac condition.
 - An arrhythmic heart condition requiring medical therapy.
8. QTcF > 450 msec, congenital long QT syndrome, second or third degree heart block at rest (with the exception of asymptomatic Mobitz type I second degree heart block).
9. Received an investigational drug within 30 days or 5 half-lives, whichever is longer, of signing the ICF.
10. Heavy smoker (defined as smoking more than 10 cigarettes/day or its nicotine equivalent including e-cigarettes).

11. Unlikely to comply with the study procedures.
12. Other medical, psychological or addictive condition that, in the opinion of an Investigator, would confound or interfere with evaluation of safety and/or PK of the investigational drug, prevent compliance with the study protocol, or preclude informed consent.
13. Participants who do not have a TCD window (Part B and Part C only) (ie, participants who are unable to have a TCD due to skull ossification).
14. For Part C only, prior participation in Part B.
15. Active symptomatic COVID-19 infection.

In addition, for Part D only:

16. Body weight < 5 kg for 1 month prior to the screening visit and at the screening visit.
17. Any condition affecting drug absorption, such as major surgery involving the stomach or small intestine (prior cholecystectomy is acceptable).

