### **8.3.2. Adverse Events**

Adverse events reported for participants participating in this study will be graded using the National Cancer Institute's (NCI) Common Terminology Criteria for Adverse Events (CTCAE), version 4.03. All AEs will be coded using the using MedDRA, version 20.0.

TEAE summary tables in both Part A and Part B will exclude sickle cell disease (SCD) related events defined as preferred terms of: combined acute chest syndrome and pneumonia, sickle cell anemia with crisis, osteonecrosis, and priapism. Additional select TEAE tables (Part B only) will summarize SCD related events which only include the preferred terms of acute chest syndrome and pneumonia (combined), sickle cell anemia with crisis, osteonecrosis, and priapism.

An overall summary will be presented which includes the number of TEAEs and the number and percentage of participants who experienced at least one TEAE. This summary will also include TEAEs Grade 3 or greater, TEAEs possibly/probably related to study drug, TEAEs leading to study drug reduction, TEAs leading to discontinuation of study drug, serious adverse events (SAEs), and deaths.

Additional summaries of TEAEs will be provided showing the number and percentage of participants who experienced at least one TEAE. These summaries will be presented by system organ class (SOC), preferred term (PT) and maximum severity. If a participant reports the same PT multiple times within the same SOC, that PT will only be counted once within that SOC for

that participant. As with the PT, if a participant reports multiple conditions within the same SOC, that SOC will only be counted once for that participant. In the summary, SOC will be listed in ascending alphabetical order; PTs will be listed in order of descending frequency for all participants within each SOC.

The occurrence of TEAEs possibly/probably related to GBT440 will be tabulated by SOC, PT and maximum severity. Serious adverse events will be presented by system organ class (SOC), preferred term (PT) and maximum severity.

Adverse events recorded in the eCRF which began prior to first dose of study drug will not be included in the summary tables.

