### 7.3.2. Adverse Events

Adverse events reported for subjects participating in this study will be graded using the National Cancer Institute's (NCI) Common Terminology Criteria for Adverse Events (CTCAE), version 4.03. All AEs will be coded using MedDRA (current version).

All adverse events summaries described below will be presented for both non-SCD and SCD-related TEAEs.

Non-SCD-related TEAE summary tables will exclude sickle cell disease (SCD) related events defined as preferred terms of: acute chest syndrome, pneumonia, pneumonia necrotising, sickle cell anemia with crisis, osteonecrosis, and priapism. Additional TEAE tables will summarize the aforementioned SCD related events.

Overall summaries will be presented which includes the number of TEAEs and the number and percentage of subjects who experienced at least one TEAE. The summaries will also include TEAEs Grade 3 or greater, TEAEs possibly/probably related to study drug, TEAEs leading to study drug reduction, TEAEs leading to study drug interruption, TEAEs leading to discontinuation of study drug, serious adverse events (SAEs) and SAEs possibly/probably related to study drug. TEAEs leading to deaths will be summarized together regardless if they are SCD-related as cause of death may include multiple TEAEs.

Additional summaries of TEAEs will be provided showing the number and percentage of subjects who experienced at least one TEAE. These summaries will be presented by system organ class (SOC), preferred term (PT) and maximum severity. If a subject reports the same PT multiple times within the same SOC, that PT will only be counted once within that SOC for that subject. As with the PT, if a subject reports multiple conditions within the same SOC, that SOC will only be counted once for that subject. In the summary, SOC will be listed in ascending alphabetical order; PTs will be listed in order of descending frequency for all subjects within each SOC.

The occurrence of TEAEs possibly/probably related to voxelotor will be tabulated by SOC, PT and maximum severity. Serious adverse events will be presented by system organ class (SOC), preferred term (PT) and maximum severity.

Grouped terms for rash and abdominal pain are summarized by PT.

Adverse events recorded in the eCRF which began prior to first dose of study drug will not be included in the TEAE summary tables.

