## 8.2. Efficacy Analysis

All efficacy data will be summarized using the EE population.

Hematology and hemolysis parameters (hemoglobin, reticulocyte count, indirect bilirubin, and LDH) will be summarized at Week 24 and Week 48 in addition to each visit for observed values and changes (absolute and percent, as appropriate) from baseline using appropriate descriptive statistics. If indirect bilirubin is missing and direct and total bilirubin are collected, indirect can be calculated as:

$$\text{Indirect Bilirubin} = \text{Total Bilirubin} - \text{Direct Bilirubin}.$$

Hb response, defined as an increase in Hb  $> 1$  g/dL, will be summarized descriptively at Week 24 and Week 48 with 95% confidence intervals provided for the response rates. Subjects who drop-out early or do not have a Week 24 or Week 48 assessment, are not included in the analysis for Hb response. Additional response assessments at each visit will be summarized descriptively. No missing data imputation or adjustment for RBC transfusion will be performed for this endpoint.

Additionally, Hb response at Week 24 and Week 48 with 95% confidence intervals will be summarized using the treated population. All subjects treated will be included in the denominator for Hb response, and subjects without a Week 24 or Week 48 assessment will be counted as non-responders at each relevant timepoint.

For subjects who had a Hb response at least 1 visit, the time to the first response will be summarized descriptively (ie, median, first quartile, third quartile, and range).

The annualized incidence rates for VOC and stroke and the associated 95% CIs will be presented. Annualized rate is defined as the total number of events divided by total person years. Total person-years is defined as the sum of subject treatment period in years which covers the time from first dose to last dose. VOC is defined based on clinical review of adverse event MedDRA preferred terms (eg, sickle cell anemia with crisis, acute chest syndrome, and pneumonia).

Exploratory analysis for change from baseline to Weeks 24 and 48 in height, weight, and head circumference, will be summarized using continuous descriptive statistics at each visit.

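### Part D's closed list of SCD-related preferred terms omits dactylitis and splenic sequestration, so such events coded to their own terms would be tabulated as non-SCD

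*SAP*

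**What the plan says.** The Part D primary endpoint is TEAEs and SAEs (Part D SAP 4.1; Protocol 3.9.4.1). Part D SAP 8.3.2 states how they are displayed: "All adverse events summaries described below will be presented for both non-SCD and SCD-related TEAEs". It then fixes the dividing line by naming the "related events defined as preferred terms of: acute chest syndrome, pneumonia, sickle cell anemia with crisis, osteonecrosis, and priapism". The list has no "eg"-type opening and no clinical review step. The one stated exception to the split is TEAEs leading to death, which are shown together.

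The other two SAPs use nearly the same list. Parts A/B (8.3.2): "combined acute chest syndrome and pneumonia, sickle cell anemia with crisis, osteonecrosis, and priapism". Part C (7.3.2): "acute chest syndrome, pneumonia, pneumonia necrotising, sickle cell anemia with crisis, osteonecrosis, and priapism".

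The protocol describes the disease at this age as follows (1.1): "Pain is also an important component of the disease and in young children, presents as dactylitis or hand-foot syndrome". Exclusion criterion 1 (Protocol 4.2) names four acute events: VOC, ACS, "Splenic sequestration crisis" and dactylitis.

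The Part D VOC rate, a secondary endpoint, is built differently. Part D SAP 8.2 defines VOC by clinical review of preferred terms and gives examples only: "eg, sickle cell anemia with crisis, acute chest syndrome, and pneumonia".

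**The concern.** Separating SCD-related from non-SCD events keeps expected disease events apart from everything else. That works only if the list covers the disease events of the age group being studied. The Part D list has the same terms as one used for participants aged 6 to 17. It keeps osteonecrosis and priapism but has no entry for the pain syndrome that the protocol itself associates with young children. It also has none for splenic sequestration, which the protocol treats as an acute event of the same standing as VOC and ACS.

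At stake is how the primary safety tables of a small descriptive cohort are read. Disease events would appear among the non-SCD TEAEs and SAEs, and the SCD-related tables would be short by the same events.

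**Working it through.** The plan gives no figure to reproduce. Part D has no power calculation and no assumed event rate (Part D SAP 6.1). The check compares lists and then shows the scale.

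**Step 1: the lists across parts.**
- Parts A/B: acute chest syndrome and pneumonia (combined), sickle cell anemia with crisis, osteonecrosis, priapism.
- Part C: the same terms plus necrotising pneumonia.
- Part D: the same five terms as Parts A/B.

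None of the three lists contains dactylitis or splenic sequestration.

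**Step 2: exclusion criterion 1 against the Part D list.**

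| Acute event in criterion 1 | Term on the Part D list |
|---|---|
| ACS | acute chest syndrome |
| VOC | sickle cell anemia with crisis (given as a VOC example in Part D SAP 8.2) |
| Splenic sequestration crisis | none |
| Dactylitis | none |

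**Step 3: how an event reaches a table.** Protocol 9.3.1 asks sites to record a known diagnosis instead of its signs and symptoms, so an entry of dactylitis is plausible. If it is coded to its own preferred term, 8.3.2 sends it to the non-SCD tables. If it is coded as sickle cell anemia with crisis, it goes to the SCD-related tables. The SAP states no rule for this case; its only grouped terms are for rash and abdominal pain. The documents therefore do not settle which route applies.

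**Step 4: consistency within the Part D SAP.** Under 8.2, clinical review may count dactylitis as VOC. Under 8.3.2, the same event, coded to its own term, would be a non-SCD TEAE.

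**Step 5: scale per child.** Inputs: about 30 children in Part D, at least 10 of them under 2 years (Protocol 3.1.4). One child moves a proportion by 100/n:
- n = 30: 100/30 = 3.3 percentage points.
- n = 10: 100/10 = 10 percentage points.

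This applies directly to the preferred-term row. The any-TEAE row of the non-SCD table moves only for a child with no other non-SCD TEAE.

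**Step 6: how many children.** The documents give no incidence. Assume that a proportion p, from 5% to 30%, of children have at least one such event coded to its own term, independently of each other. The expected number is n × p, and the chance that at least one child is affected is 1 − (1 − p)^n.

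| n | p | Expected children | Chance of at least one |
|---|---|---|---|
| 30 | 5% | 1.5 | 79% |
| 30 | 30% | 9 | over 99% |
| 10 | 5% | 0.5 | 40% |
| 10 | 30% | 3 | 97% |

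These figures illustrate the assumed range; they are not estimates from the trial.

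**The case against.** The best defence is that the primary endpoint is undamaged. It carries no SCD restriction, both sets of tables are produced, and an event of dactylitis would be visible under its own preferred term. Events judged possibly or probably related to voxelotor are tabulated separately, and Protocol 9.2.3 lets the investigator attribute an event to underlying disease. Nothing is tested, so no decision rule turns on the split. All of this stands. It limits the point to misclassification between displayed tables, and it means one cannot say that the non-SCD tables must be read as the drug's profile. It does not explain why a closed list for this age group should leave out events that the protocol names as part of the disease.

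The dependence on coding also stands. Misplacement is conditional, and the weakness is that the SAP does not exclude it.

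Three stronger readings are tempting and are not supported.
- A reader might infer that the VOC rate is understated by the share of episodes recorded as dactylitis. The 8.2 definition is open and settled by clinical review, so nothing excludes dactylitis, and the documents give no such share. Criterion 1 also lists VOC and dactylitis separately, so counting one as the other is a matter of definition.
- A reader might call this an adolescent list. The same terms served Part A, which included ages 6 to 11.
- A reader might describe both omitted events as typical of infants. The documents say this of dactylitis in young children. For splenic sequestration they support only that it is an acute event named beside VOC and ACS, and that splenic function is lost early (Protocol 1.1).

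**Conclusion.** The point holds as a classification fault in Part D SAP 8.3.2. Applied as written, the closed list places dactylitis and splenic sequestration, when coded to their own preferred terms, among the non-SCD TEAEs and SAEs. The non-SCD tables are then overstated and the SCD-related tables understated by the same children.

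The size is 3.3 points per child in the affected preferred-term row at N = 30, and 10 points in an age group of 10. The effect on the any-TEAE row may be nil. How many children are affected is unknown from the documents. The conclusion rests on two conditions: that such events occur in Part D, and that they are not coded as sickle cell anemia with crisis. No event drops out of the primary endpoint, and the VOC endpoint is not shown to be wrong. The correction is still worth making, because it concerns the primary endpoint tables and costs almost nothing.

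**What to change.** Before database lock, add the preferred terms for dactylitis and splenic sequestration to the SCD-related list in Part D SAP 8.3.2, and footnote the tables to say that the list differs from those of the other parts. The VOC definition in 8.2 needs no change on this account.

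The cost is one line in the SAP, the matching programming list and the footnote. Comparability between parts is hardly affected, since the Part C list already differs from the other two. Timing matters more than effort: the study is open-label, and moving terms between tables after the final data have been reviewed would be a post hoc change to the primary safety display.
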